8.2 Serious adverse event reporting

To ensure patient safety, every SAE, regardless of suspected causality, occurring after the patient has provided informed consent and until 30 days after the patient has stopped study participation (defined as time of last dose of study drug taken or last visit whichever is later).

Any SAEs experienced after this 30 day period should only be reported to Novartis if the investigator suspects a causal relationship to the study drug.

8.3 Pregnancies

To ensure patient safety, each pregnancy in a patient on study drug must be reported to Novartis within 24 hours of learning of its occurrence. The pregnancy should be followed up to determine outcome, including spontaneous or voluntary termination, details of the birth, and the presence or absence of any birth defects, congenital abnormalities, or maternal and/or newborn complications.

9 Data review and database management

9.1 Data collection

Patient data will be collected/retained within our transplant patient database as per our normal operating procedure and thus immediately available and retrievable for subsequent analyses. The data is housed within the Ohio State University Medical Centers Transplant server located in a locked, secure facility.

9.2 Database management and quality control

Permanent patient electronic records will be stored and maintained on the Transplant server housed in a locked, secure facility. Study patient data will be subject to the same quality controls already in place for all patients treated by the Ohio State University Medical Centers Transplant Program.

10 Data analysis (Any or all sections may be included based on type of study)

10.1 Analysis of the primary objective(s)

10.1.1 Variable

The primary endpoint consists of non-death censored graft survival and biopsy proven acute rejection at 1 year post-transplant. These events will be directly measured and not calculated.

10.1.2 Statistical hypothesis, model, and method of analysis

The primary endpoint will be a composite endpoint of graft survival (non-death censored) and biopsy proven acute rejection at 1 year.

Secondary endpoints at 6 months, 1, 2 and 3 years will include: graft survival and patient survival/death at 2 and 3 years, rate and grade of acute cellular rejection, rate of acute antibody mediated rejection, rate of new donor specific antibody formation, estimated CrCl by MDRD, lipid control as determined by requirement for anti-lipid medications and average levels with and without medications, ability to maintain initial immunosuppressive medications and reason for switch if required, wound complications as determined by need for wound packing, infection treatment with antibiotics, presence of hernia on exam and requirement for hernia repair, as well as presence of symptomatic lymphocele, and New Onset Diabetes After Transplant as determined by need for new oral or sustained Insulin medication.

Statistical analysis will be performed on SPSS or STATA software with dichotomous variables evaluated by Chi-Squared analysis, continuous variables by Student's T-Test, non-parametric outcomes will be assessed by Wilcoxon rank sum test (Mann-Whitney U test). Kaplan-Meier survival curves with log rank tests will be used to determine a difference in graft and patient survival over time.

Safety data will include patient and graft survival, biopsy proven acute rejection, and hospital admissions.

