3.3 Exploratory objectives

4 To explore the kidney and vascular endothelial function assessed by a panel of molecular markers over the observation period. Study design

Randomized, single center parallel-group, open-label study.

Pilot study with exploratory objectives.

Eligibility: All primary or retransplant recipients of deceased donor or living donor grafts with negative crossmatch who are felt to have good expectations for renal function recovery after surgery will be offered entry into the study.

Treatment scheme is as described above, with Solumedrol 500 mg IV in OR as induction, then 5 doses of Thymoglobulin starting morning of POD 1 at 1.25 mg/dose (rounded to nearest 25 mg) with rapid steroid taper over five doses. The mTOR inhibitor drug will be started on POD 0 and Neoral introduced as renal function recovers, usually starting on POD 2.

Measurement/Assessments: as described above, graft and patient survival per standard definitions, clinically indicated biopsies for determination of acute cellular or antibody mediated rejection, renal function as estimated from serum Cr based on MDRD, clinic visits for wound assessment, standard of care labs for renal function, bone marrow function (WBC and platelet count), liver function, lipid panel, donor specific antibody determination during any significant increase in serum Cr, drug levels routinely monitored for need of number of dose adjustments and compliance, Emergency Room and hospitalizations, as well as unscheduled clinic and other physician visits. For the pilot study, we would perform scheduled CMV, EBV and serum BK PCRs monthly for the first year, then quarterly or with any viral symptoms.

A subset of patients will have coded plasma samples sent to clinical research and development at the University of Colorado. These biomarker samples will be used to assess vascular endothelial dysfunction and inflammation markers as well as kidney dysfunction markers.

Plasma samples are collected and stored at The Ohio State University Wexner Medical Center tissue typing lab per standard of care.

5 Population

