6.2 Treatment arms

Patients will be assigned to one of the following “n” treatment arms in a ratio of 2:1; Zortress or Sirolimus started on POD 0, with Solumedrol 500 mg IV in OR as induction, then 5 doses of Thymoglobulin starting morning of POD 1 at 1.25 mg/dose (rounded to nearest 25 mg) with rapid steroid taper over five doses. Neoral will be introduced as renal function recovers, usually starting on POD 2. We will enroll a total of 60 patients.

- Zortress and Neoral, with Thymoglobulin induction and perioperative steroids
- Rapamycin and Neoral, with Thymoglobulin induction and perioperative steroids

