7.1 Table 7-1

Assessment schedule:

Visit number	1 Screening/ Baseline	2	3	4	5	6	7	8	9	10	11	12	13	14	15	16	17	18
Time of Visit		Day 0	Day 1	Day 2	Day 3	Day 4	Day 5 ¹	Day 6 ¹	Day 7 ¹	Wk 2	Mo 1	Mo 2	Mo 3	Mo 6	Mo 12	Mo 18	Mo 24	Mo 36
Inclusion/Exclusion criteria	X																	
Informed consent	X																	
Physical examination	X	X	X	X	X	X	X	X	X	X	X	X	X	X	X	X	X	X
Demographics	X																	
Medical History	X																	
Pregnancy Test ²	X																	
Vital signs	X	X	X	X	X	X	X	X	X	X	X	X	X	X	X	X	X	X
Hematology		X		X				X	X	X	X	X	X	X	X	X	X	X
Chemistry		X			X			X	X	X	X	X	X	X	X	X	X	X
Lipid panel	X									X	X	X	X	X	X	X	X	X
24 hour urine												X	X	X	X	X	X	X
Alloscreen	X															X		
Flow Crossmatch	X															X		
HGB A1C																X		X
Kidney Biopsy	X															X		
Adverse events		X	X	X	X	X	X	X	X	X	X	X	X	X	X	X	X	X
Cyclosporine level ³				X				X	X	X	X	X	X	X	X	X	X	X
Everolimus level ³					X			X	X	X	X	X	X	X	X	X	X	X
Optional sub study: Plasma for Biomarkers ⁴	X				X			X	X	X	X	X	X	X	X	X	X	X

Legend:

- 1: If still inpatient
- 2: Females capable of childbearing
- 3: Cyclosporine and Zortress levels are monitored twice weekly for 0-3 months post-transplant, every two weeks for 3-12 months post-transplant, and monthly greater than 1 year post-transplant.
- 4: Plasma for biomarkers will be assessed at the University of Colorado in a subset of patients using existing plasma samples.

Patients will be followed as per the standard of care at this transplant center (The Ohio State University Medical Center, Division of Transplantation). Additional study procedures include a protocol biopsy at month 12 and some additional laboratory work at screening/baseline and at months 6, 12, 24, and 36.

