10.1.3 Handling of missing values/censoring/discontinuations

Patients lost to follow-up or discontinued from the study will be censored from further analysis at the time of their withdrawal from the study.

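### New donor-specific antibody rates are planned at four times, but the only stated test trigger is a creatinine rise and no antibody test is named at 6 months, 2 years or 3 years

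*Combined protocol and SAP*

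**What the plan says.** Section 10.1.2, repeated in 10.2.1, opens its list with "Secondary endpoints at 6 months, 1, 2 and 3 years will include" and includes "rate of new donor specific antibody formation". The method for such outcomes is "dichotomous variables evaluated by Chi-Squared analysis". No denominator is given.

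The Measurement/Assessments paragraph of section 4 (Study design, which runs on from heading 3.3) and the same paragraph of the synopsis give the only stated rule for this test: "donor specific antibody determination during any significant increase in serum Cr". The size of the rise is not defined.

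Table 7-1 has no row named for DSA. The nearest rows, Alloscreen and Flow Crossmatch, are each marked at baseline and at one later visit. The text under the table adds "some additional laboratory work at screening/baseline and at months 6, 12, 24, and 36" without naming the tests.

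The missing-data rule in section 10.1.3 is "Patients lost to follow-up or discontinued from the study will be censored from further analysis". It does not cover a patient who is still in follow-up but was not tested.

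**The concern.** A rate at a fixed time needs either a test in everyone at that time or a stated rule for those not tested. Here the one explicit rule tests patients whose creatinine has risen. Antibody that forms while creatinine is stable would not be found by that rule.

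The trigger is also not neutral between arms. Serum creatinine and estimated GFR are compared outcomes (sections 3.2, 10.1.2 and 10.2.1). If the two drugs affect creatinine differently, the chance of being tested differs by arm even when antibody formation does not. The trial is open-label (section 6.4) and the trigger has no threshold, so the decision to test is made with the arm known.

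At stake is whether a reported DSA rate, or a difference between arms, describes antibody formation or testing practice. The primary endpoint is not affected.

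**Working it through.** The plan gives no DSA rate or power figure to reproduce. The check has two parts.

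**1. Endpoint times against scheduled tests**

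| Endpoint time | Antibody-type test marked in Table 7-1 | Other provision |
|---|---|---|
| 6 months | none | unnamed laboratory work |
| 1 year | possibly Alloscreen and Flow Crossmatch | unnamed laboratory work |
| 2 years | none | unnamed laboratory work |
| 3 years | none | unnamed laboratory work |

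In the table text available, the later Alloscreen and Flow Crossmatch marks fall under month 18. The Kidney Biopsy mark falls in the same column, yet the text under the table puts the protocol biopsy at month 12. The column may have shifted in conversion from PDF, so this is not counted as an error. If the visit is month 12, one of the four endpoint times has a scheduled antibody-type test. If it is month 18, none has.

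**2. What creatinine-triggered testing does to a rate (illustration only)**

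Let p be the true rate of new DSA, a the probability of being tested if DSA is present, and b the probability of being tested if it is absent. None of these is in the documents; all values below are assumptions.

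- All patients as denominator: p × a.
- Tested patients as denominator: p × a / [p × a + (1 − p) × b].

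| p | a | b | Of all patients | Of those tested |
|---|---|---|---|---|
| 10% | 50% | 20% | 5.0% | 0.05/(0.05 + 0.18) = 21.7% |
| 10% | 60% | 30% | 6.0% | 0.06/(0.06 + 0.27) = 18.2% |
| 15% | 50% | 20% | 7.5% | 0.075/(0.075 + 0.17) = 30.6% |
| 15% | 60% | 30% | 9.0% | 0.09/(0.09 + 0.255) = 26.1% |
| 20% | 50% | 20% | 10.0% | 0.10/(0.10 + 0.16) = 38.5% |
| 20% | 60% | 30% | 12.0% | 0.12/(0.12 + 0.24) = 33.3% |

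The same data give 5% to 12% or 18% to 38%, depending only on the denominator. The first is below the true rate whenever a is less than 1. The second is above it only when a exceeds b; if a equals b it returns p.

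For the arm comparison, "We will enroll a total of 60 patients" "in a ratio of 2:1" gives 40 on Zortress and 20 on Rapamune. Take p = 20% in both arms, with a = 30% on Zortress and 60% on Rapamune:

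- Of all patients: 0.20 × 0.30 = 6% against 0.20 × 0.60 = 12%, a false difference of 6 points. The expected positives are 40 × 0.06 = 2.4 and 20 × 0.12 = 2.4.
- Of those tested, with b = 20% in both arms: 0.06/(0.06 + 0.16) = 27% against 0.12/(0.12 + 0.16) = 43%.

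So a tested-only denominator does not remove the problem when testing is for cause.

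The formulas ignore the one scheduled Alloscreen visit. They apply most directly at 6 months. A cumulative 2- or 3-year rate would also include antibody found at that visit, if Alloscreen identifies DSA.

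**The case against.** The strongest reply is that the unnamed laboratory work falls at months 6, 12, 24 and 36, exactly the four endpoint times, and may be meant to include DSA. Section 4 also says plasma is stored in the tissue typing laboratory as standard of care, and the stated creatinine trigger is not said to be the only occasion for testing. This stands in part. It rules out saying that the endpoint cannot be measured, or that stable patients are never tested. It does not close the point, because no document names a DSA test at 6 months, 2 years or 3 years, and the biomarker row that marks late plasma samples belongs to an optional substudy in a subset.

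A reader might infer that untested patients count as negative and that the rates will therefore be too low. The documents do not say so. They give no rule for untested patients, and a tested-only denominator could push the rate up.

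A reader might also take Alloscreen as the DSA test. The plan never defines it. If it does not identify donor-specific antibody, no DSA test is scheduled at all.

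Finally, the endpoint is minor. It is absent from the objectives in section 3.2 and from section 7.5.1, all objectives are called exploratory, and the study is stated not to be powered. This limits the weight of the point, but a descriptive rate still needs a known denominator and a known way of finding cases.

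**Conclusion.** The point holds in a limited form. No DSA test is named at 6 months, 2 years or 3 years, and at most one of the four endpoint times (1 year) has a scheduled antibody-type test for all patients. Unless the additional laboratory work includes DSA, rates at the unscheduled times reflect creatinine-triggered testing. The direction of bias depends on a denominator that the plan does not state, and the bias can differ by arm.

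The documents support no numerical size. The ranges of 5% to 12% and 18% to 38%, and the false 6-point difference, rest wholly on assumed rates and testing probabilities. Differential testing by arm is a possibility, not something the documents show. With 2.4 expected positives per arm in that example, a chi-squared result could not separate antibody formation from testing. The consequence is confined to one exploratory secondary endpoint.

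**What to change.** In sections 10.1.2 and 10.2.1:

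1. State whether the laboratory work already planned at months 6, 12, 24 and 36 includes DSA. Confirm whether Alloscreen identifies donor-specific antibody and which month its post-transplant visit belongs to. Make Table 7-1 agree.
2. Compare arms for new DSA only at visits where every patient has a scheduled test: the post-transplant Alloscreen against baseline, if confirmed, plus months 6, 12, 24 and 36 if that work includes DSA. Use patients tested as the denominator.
3. At all other times, retitle the endpoint *DSA found on for-cause testing*. Report it descriptively, without a chi-squared comparison, giving the number tested and the number positive per arm.

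This is a change of wording and adds no assays. The cost is possibly fewer time points for one exploratory secondary endpoint. If the sponsor wants a comparison at all four times and the planned laboratory work does not include DSA, a test for all patients would have to be named at each time, at assay cost.

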- Results of 12 month surveillance biopsies
- Lipid panels and use of lipid lowering medications at 1 year after transplant
- Incidence of MI and CHF at 1 and 3 years after transplant

- Incidence of wound infection at 1 year after transplantation
- Incidence of lymphocele at 1 year after transplantation
- Plasma concentrations of S-adenosyl homocysteine (SAH) and S-adenosyl methionine (SAM) Plasma concentrations of endothelial dysfunction markers (symmetric and asymmetric dimethyl arginine (SDMA, ADMA), L-arginine, L-citrulline, L-ornithine, cysteine, and homocysteine over the observation period
- Plasma concentrations of bioactive lipids (HODEs, HEPEs, HETEs, and prostaglandins) over the observation period
- Plasma protein patterns

Data analysis: The incidence of graft loss, patient death, and acute rejection will be compared by chi squared analyses. Patient and graft Kaplan-Meier survival curves will be compared by log rank test. We hypothesize there will be no statistically significant difference between the treatment arms. As this is a pilot study, it was not statistically powered to detect subtle differences in outcome. All continuous variables such as serum creatinine, cGFR, serum lipids, WBC, platelets, etcetera will be compared by student's t test. Any other dichotomous variables will be compared by chi squared analysis.

1 Background

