3.2 Secondary objectives

Secondary outcomes would include factors involved with adverse events and tolerability and would include: renal graft survival (non-death censored) and biopsy proven acute rejection at 6 months, 2 and 3 years, as well as the number and grade of acute rejection episodes and responsiveness to treatment, serum creatinine and estimated GFR, results of renal biopsies at 12 months post-transplant to look for histological evidence of graft injury, early and late wound complications, infections including CMV, EBV and BK infections as monitored by serum PCR testing, lipid panel testing, particularly triglycerides, cardiac events such as acute myocardial infarctions or Congestive Heart Failure episodes, and tolerability of the Neoral and mTOR combination as determined by the patients who required conversion off of the intended randomized drug combination, with attempt to document why the patient did not tolerate the drug combination. All objectives are exploratory in nature as this is a pilot study.

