The patient population will be all adults (18-75 years of age) who receive a living donor or deceased donor renal transplant as a first or subsequent renal transplant procedure only (no extra-renal organ transplant recipients). We will invite any patient who would normally be considered for our current Sirolimus®/ Neoral® protocol with Thymoglobulin® and steroid induction to consent for this pilot study and then undergo randomization post-operatively if the transplant surgeon anticipates normal early graft function. If there were significant concerns for prolonged graft dysfunction, then the patients will not be invited into the pilot study. Invited patients would include anyone currently not on steroids prior to transplantation, and those with no known intolerance to any of the drugs mentioned. Patients must also be willing to perform the expectations of the study protocol reliably.

This will be a single center pilot study performed at The Ohio State University Comprehensive Transplant Center. Our center performs approximately 100 to 110 living donor and 90 to 100 deceased donor renal transplants per year. If we assume that at least 150 patients per year qualify for the study, then a conservative estimate of 75 enrolled patients a year is possible. We would propose to enroll a total of 60 patients over 12 months, and then follow these patients for a complete 3 years. We will randomize 2:1 Zortress to Sirolimus using a random number generator.

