6.3 Treatment assignment

Randomization will be stratified by type of donor kidney received (living or deceased donor kidney) and primary versus retransplant recipient. Randomization will be performed using a random number generator.

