10.2 Analysis of secondary objectives

10.2.1 Efficacy (secondary)

Secondary endpoints at 6 months, 1, 2 and 3 years will include: graft survival and patient survival/death at 2 and 3 years, rate and grade of acute cellular rejection, rate of acute antibody mediated rejection, rate of new donor specific antibody formation, estimated CrCl by MDRD, lipid control as determined by requirement for anti-lipid medications and average levels with and without medications, ability to maintain initial immunosuppressive medications and reason for switch if required, wound complications as determined by need for wound packing, infection treatment with antibiotics, presence of hernia on exam and requirement for hernia repair, as well as presence of symptomatic lymphocele, and New Onset Diabetes After Transplant as determined by need for new oral or sustained Insulin medication.

Statistical analysis will be performed on SPSS or STATA software with dichotomous variables evaluated by Chi-Squared analysis, continuous variables by Student's T-Test, non-parametric outcomes will be assessed by Wilcoxon rank sum test (Mann-Whitney U test). Kaplan-Meier survival curves with log rank tests will be used to determine a difference in graft and patient survival over time.

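### Lipids are compared by unadjusted two-sample tests although the screening lipid panel and the donor-type stratum are available: a cheap precision gain that is nil to small unless screening and follow-up lipids correlate at about 0.5 or more

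*Combined protocol and SAP*

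**What the plan says.** The synopsis (Data analysis) states: "All continuous variables such as serum creatinine, cGFR, serum lipids, WBC, platelets, etcetera will be compared by" Student's t-test. Sections 10.1.2 and 10.2.1 give the same plan, "with dichotomous variables evaluated by Chi-Squared analysis, continuous variables by" the t-test, and add the Wilcoxon rank sum test for non-parametric outcomes. No adjusted or stratified analysis appears anywhere.

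Two pieces of pre-treatment information are available:
- Section 6.3: "Randomization will be stratified by type of donor kidney received (living or deceased donor kidney) and primary versus retransplant recipient".
- Table 7-1 marks the lipid panel at Visit 1 (Screening/Baseline) and from week 2 to month 36. The text below the table mentions "some additional laboratory work at screening/baseline and at months 6, 12, 24, and 36". The lipid exclusion in section 5.2 cannot be checked without cholesterol and triglycerides, so nearly every patient should have a screening value.

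Section 3.2 names "lipid panel testing, particularly triglycerides" and estimated GFR among the secondary outcomes. Section 5 (Population) sets 60 patients and says: "We will randomize 2:1 Zortress to Sirolimus using a random number generator".

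The lipid outcome is described in two ways. The synopsis (Other assessments) lists "Lipid panels and use of lipid lowering medications at 1 year after transplant". Section 10.2.1 lists "lipid control as determined by requirement for anti-lipid medications and average levels with and without medications" and does not say whether the arms are to be compared within the groups with and without medication.

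**The concern.** With about 20 control patients, any lipid comparison will be imprecise. A screening value that predicts the follow-up value removes part of the between-patient variation, and this one is already being collected. A t-test on follow-up values alone leaves it unused. Section 1 says the secondary interest is to characterise the everolimus side-effect profile against sirolimus, and that depends on how precisely differences are estimated.

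The with-and-without-medication wording adds a smaller risk. Lipid drugs can be started or changed after randomisation, so comparing arms within groups defined by their use would no longer be a randomised comparison. The plan does not rule this out.

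**Working it through.** **Inputs from the documents.** N = 60 and 2:1 allocation (section 5) give 40 v 20. Sections 10.3 and 10.4 give no power, SD or effect size, so there is no planned figure to reproduce.

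**Assumed.** Two-sided alpha of 0.05; a difference of 0.6 SD as a yardstick; r from 0 to 0.7; donor type unrelated to lipids; all 60 analysed.

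**Unadjusted t-test.** SE = sqrt(1/40 + 1/20) = 0.274 SD, with 58 df. Noncentrality is 0.6/0.2739 = 2.191 and power is 0.577. The difference detectable with 80% power is 0.780 SD.

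**ANCOVA with q = 2 covariates (donor type, screening value).** The variance is multiplied by (1 − r²) × [1 + q/(N − q − 3)] = (1 − r²) × (1 + 2/55) = (1 − r²) × 1.036, with 60 − 2 − 2 = 56 df. The second factor charges for chance covariate imbalance.

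| r | Variance factor | SE (SD units) | Power at 0.6 SD | Detectable at 80% power (SD) |
|---|---|---|---|---|
| 0 | 1.036 | 0.279 | 0.562 | 0.795 |
| 0.2 | 0.995 | 0.273 | 0.579 | 0.779 |
| 0.3 | 0.943 | 0.266 | 0.602 | 0.758 |
| 0.5 | 0.777 | 0.241 | 0.685 | 0.688 |
| 0.7 | 0.529 | 0.199 | 0.842 | 0.568 |

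Break-even on variance: (1 − r²) × 57/55 = 1, so r² = 2/57 and r is about 0.19. At r = 0 the loss is 0.577 − 0.562 = 0.015.

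**Simulation check (10,000 trials per case, same model).** At r = 0, 0.2, 0.3, 0.5 and 0.7, power is 0.556, 0.573, 0.596, 0.670 and 0.830 under simple 2:1 randomisation, and 0.568, 0.586, 0.617, 0.694 and 0.848 when allocation is balanced within donor type. The formula lies between the two throughout.

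**Truncated entry values.** If the section 5.2 lipid exclusion removes the top 2–10% of a normal baseline (assumed), r = 0.3, 0.5 and 0.7 falls to 0.26–0.28, 0.44–0.48 and 0.64–0.68.

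**Change from baseline instead.** Its variance factor is 2(1 − r), which exceeds 1 when r is below 0.5. Simulated power (balanced) is 0.398, 0.451, 0.578 and 0.794 at r = 0.2, 0.3, 0.5 and 0.7, below ANCOVA every time.

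**eGFR with donor type added.** R² = p(1 − p)D²/[p(1 − p)D² + s²], where D is the living–deceased gap and s the within-group SD in mL/min. All values are assumed, with p = 0.5. Power at 0.6 SD, t-test to adjusted model, by simulation:

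| D, s | R² | Balanced within donor type | Simple 2:1 |
|---|---|---|---|
| 10, 18 | 25/349 = 0.072 | 0.581 to 0.613 | 0.567 to 0.592 |
| 5, 18 | 6.25/330.25 = 0.019 | 0.580 to 0.590 | 0.581 to 0.579 |
| 3, 20 | 2.25/402.25 = 0.006 | 0.577 to 0.582 | 0.574 to 0.567 |

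No calculation was made for creatinine.

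**The case against.** The strongest reply is that this is a preference about efficiency and not an error. Section 3.2 calls all objectives exploratory, sections 10.3 and 10.4 disclaim power, and the plan sets no target that the t-test fails to meet. That stands, and it is why the point is minor.

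Second, r may well be low. Entry values are truncated, new immunosuppression starts at transplantation, and lipid drugs may be added. At r = 0.2 the gain is nil. With an assumed 15% loss (34 v 17, simple allocation), simulated power goes from 0.510 to 0.493 at r = 0 and from 0.520 to 0.516 at r = 0.2. This stands too, but the trade is uneven: about 0.015 to lose, against about 0.11 to gain at r = 0.5 and 0.26 at r = 0.7.

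Third, triglycerides are probably skewed and the plan already offers the Wilcoxon test. The lipid figures here compare ANCOVA with a t-test on normal data, so no gain over Wilcoxon has been shown.

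A reader might also infer that the planned tests are biased, or that the t-test is conservative because it ignores the strata. The documents support neither. Omitting a baseline covariate from a randomised comparison does not bias it. Conservatism needs balance within strata, and beyond naming the strata the documents describe only a random number generator. In the eGFR example (gap 10, SD 18) the t-test's simulated size was 0.042 with balanced allocation and 0.052 with simple randomisation.

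**Conclusion.** The point holds as a cheap improvement and is minor. For lipids, adjustment is nil to small at low r and material only at r of about 0.5 or more. Nothing in the documents shows that r is that high, so a general claim of a material gain is not supported. For eGFR the expected change in power is about 0 to +0.03 over assumed gaps of 3–10 mL/min and SDs of 18–20, and can be slightly negative at the low end; creatinine is not quantified. The lipid figures rest on the assumed alpha, 0.6 SD yardstick, r, normal data and full follow-up. The primary endpoint is not affected. Ruling out a comparison within lipid-drug groups is worthwhile whatever r turns out to be.

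**What to change.** In the synopsis, 10.1.2 and 10.2.1:

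1. Compare lipids between arms at each visit by ANCOVA with arm, donor type and the screening value, using the log scale for triglycerides. Do not substitute change from baseline.
2. Make the comparison regardless of lipid-lowering drug use, report drug use by arm beside it, and label the averages with and without medication as descriptive.
3. If a screening value is missing, impute the overall screening mean, pooled across arms, so that no patient is dropped for that reason.
4. Optionally, add donor type to the eGFR and creatinine comparisons to match the stratified randomisation.

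The primary/retransplant factor is left out of the model for now: section 5.1 admits only primary recipients, while sections 5 and 6.3 provide for retransplants, and these must be reconciled first.

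Cost: text changes, including a stated choice on how lipid-drug use is handled. No new data, visits or patients are needed. The downside is one or two degrees of freedom, and about 0.015 power if screening lipids prove unrelated to follow-up lipids.
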